# Key Study Personnel

Chief Investigator			
	[name]		
	NIHR Clinical Lecturer		
	Northern Vascular Centre / Newcastle University		
Co – Investigators			
	[name]		
	Professor of trials for Older People, AGE research Group, NIHR		
	Newcastle Biomedical Research Centre		
	[name]		
	Professor of Vascular Surgery, Northern Vascular Centre, Newcastle.		
	[name], Research Fellow and Vascular Registrar,		
	Northern Vascular Centre, Newcastle.		
	[name], Academic Teaching Fellow, Northern Vascular Centre, Newcastle		
	[name] and [name]; patients with lived experience of vascular disease.		
	[name], Consultant Vascular Surgeon, Northern Vascular Centre, Freeman Hospital, Newcastle		
	[name], PhD researcher, Department of Sport, Exercise and Rehabilitation, Northumbria University		
	[name] [name], Senior Lecturer in Exercise Physiology, Department of Sport, Exercise and Rehabilitation, Northumbria University		
	The Vascular and Endovascular Research Network (VERN)		
Sponsor & Co-ordination Centre	The Newcastle upon Tyne Hospitals Foundation Trust		
Collaborators:	[name], Aneurin Bevan University, Newport [name], University Hospitals Coventry & Warickshire [name], University Hospitals of Leicester NHS Trust [name], Leeds Teaching Hospitals NHS Trust [name] / [name], Hull University Teaching Hospitals [name], Imperial College Healthcare NHS Trust [name], University Hospitals Bristol and Weston Foundation Trust [name], South Tyneside and Sunderland Hospitals		
	[name], University Hospitals Birmingham NHS Trust [name], Liverpool University Hospitals Foundation Trust [name], Belfast City Hospital [name], Royal Infirmary of Edinburgh		

Northern Vascular Centre Research Team; [name], [name], [name] and [name].

Study summary				
Full study title	A Multicentre Prospective observational study to investigate the prevalence and short-term impact of frailty, anaemia, sarcopenia and multimorbidity in chronic limb threatening ischaemia (CLTI)			
Short study title	FraiLTI - Frailty in Chronic Limb Threatening Ischaemia			
Study aim	To assess the prevalence and short-term impact of frailty, anaemia, sarcopenia and multiple long-term conditions on patients admitted with CLTI.			
Study design	Multicentre Observational Study			
Study participants	Patients admitted with all presentation of CLTI at a designated vascular centre			
Sample size	Approximately 30 from each centre of	Approximately 30 from each centre over six months (10 centres)		
Planned study period	9 months (from first recruit)			
	Objectives	Outcome Measures		
Primary	Identify the prevalence of frailty and multi-morbidity among CLTI patients using standardised assessments.	Grip strength assessment and sarcopenia on cross-sectional imaging.		
Secondary	To understand if frailty, multimorbidity and poly pharmacy are associated with adverse clinical outcomes.	1) Major-lower limb amputation rate at 3 months (limb-loss or amputation) 2) Survival at 3 months (who is alive at the three-month timepoint) 3) Re-interventions (repeat surgery or procedures) 4) Length of hospital stay 5) Discharge home 6) Re-admissions and reintervention (who is readmitted to hospital or needs further admission and procedures)		

# Summary of Research Program

This prospective project forms part of a wider research theme investigating frailty, sarcopenia, multiple long-term conditions and anaemia on outcomes following vascular and endovascular surgery. It is hoped that this research will identify areas for prospective optimization and improvement in clinical and patient-reported outcomes. FrailTI is being conducted with a team of experts and specialists in Older Peoples Medicine, sarcopenia, anaemia, anaesthesia and vascular surgery within a complementary multi-disciplinary team including physiotherapy and occupational therapists, in partnership with patients.

A particular interest within this research theme is those patients with chronic limb threatening ischaemia (CLTI). CLTI has been highlighted as a UK national priority by a recent Delphi consensus supported by the RCS England and the Vascular Society of Great Britain and Ireland (VSGBI). This identified improving the clinical outcomes for CLTI and other associated conditions (diabetic foot disease, major lower limb amputation) as top ten research priorities among vascular specialists, vascular nurses and vascular technologists. This is a pivotal first step in developing the understanding of frailty in CLTI in a UK first study. This study will provide an understanding of the scale of the problem and any clinical consequence or association for CLTI revascularisation. It is anticipated that FraiLTI data will be used in the development of large-scale prospective research aimed at benefiting the care of UK and worldwide vascular patients with CLTI.

# Background

FraiLTI (Frailty in chronic Limb Threatening Ischaemia) is a UK first, multi-centre prospective observational study evaluating the impact of frailty, sarcopenia and multi-morbidity on outcomes following vascular intervention for Chronic limb threatening ischaemia (CLTI). CLTI is a patient-led JLA priority for vascular research, as outcomes may be worse in those with multi-morbidity and potentially frailty.

Frailty, traditionally defined as an age-related multisystem decline leaves patients vulnerable to stressors such as illness, trauma or surgery. Some surgical specialties have identified that the presence of frailty is associated with inferior clinical outcomes for example, patients with frailty under-going major colorectal surgery had a worse survival and a longer stay in the intensive care unit.

A key component of frailty is sarcopenia - skeletal muscle dysfunction that develops over a period of time and typically affects older patients leading to reduced strength and muscle mass. Some evidence exists that sarcopenia alone leads to worse survival following endovascular surgery and following elective joint replacement. The association of frailty and the interaction with sarcopenia is not fully understood nor is the interaction within high risk CLTI patients.

Multiple long-term conditions (multimorbidity) is also an important factor potentially affecting outcomes. Most work to date in vascular surgery has focussed on cardiometabolic comorbidities, and there is a need to examine the impact of multimorbidity including conditions out with the central cardiovascular system. Our preliminary retrospective work has identified that both anaemia and sarcopenia (publication accepted 2021) are adversely associated with survival and limb loss following revascularization surgery for CLTI. Older patients undergoing aneurysm surgery may well be at greater risk of adverse outcome , but many patients with CLTI are relatively young and fall under the radar before proceeding to in-hospital intervention or major surgery to attempt to save limb. Multimorbidity has been shown to reduce cardiovascular quality of life (9) and worse survival in related populations such as those with heart failure patients (10))

It is postulated that CLTI patients with frailty and/or multi-morbidity, may be associated with worse outcomes, potentially independent of age. FraiLTI has been developed to assess the nationwide scale of the problem and to develop a platform on which to build future intervention studies to mitigate the impact of frailty, sarcopenia and multimorbidity in this group of patients

#### Aim

- 1. The *primary aim* of the study is to identify the prevalence of frailty, sarcopenia and multimorbidity among chronic limb threatening ischaemia (CLTI) patients.
- 2. The *secondary aim* is to identify any associations with patient led and prioritised clinical outcomes such as survival, limb-loss, cardiovascular events or re-admission as well as those with non-salvageable CLTI. This will facilitate risk prediction, modelling and identify potential targets for intervention in future prospective research.

# Study Design

This is a multi-centre prospective observational study.

# Population

All patients presenting to the vascular service with chronic limb threatening ischaemia as defined by the Global CLTI guidelines are eligible for participation, irrespective of mode or eventual plan for revascularisation

#### Recruitment

All patients admitted with CLTI to a dedicated vascular centre will be invited to participate by a member of the clinical team. Confirmation of CLTI diagnosis will be made by the admitting vascular specialist. Potentially eligible participants will be sign-posted to the relevant research team member only after the patient has suggested they would be happy/agreeable to for their details to be shared with a member of the research team on the delegation log at each site. At this point the FraiLTI researcher will approach the patients with the initial information. After a period of consideration, typically 24hours, patients will then be formally screened according to the inclusion and exclusion criteria. All presentation modes will be eligible including out-patient clinic, emergency clinic, emergency department and general practitioner referrals. This will allow the capture of the breadth of CLTI disease and give information on the mode of referral of CLTI patients in the context of frailty. Recruitment and enrolment will be performed by a vascular or surgical trainee's, research teams and wider networks as long as all research training requirements have been met.

#### Eligibility

Patients meeting the below inclusion criteria will be invited to participate in the FraiLTI study.

# Inclusion

- All adults over 18, able to consent and participate with ongoing assessments
- All chronic limb-threatening ischaemia patients as per consensus definition irrespective of mode or presentation or plan to revascularize.

# **Exclusion**

- Admissions for non-CLTI
- Unable to agree to assessments or participate in study assessments
- Pregnant women

• Under 18.

Consent

Written and verbal versions of the participant information and informed consent will be presented to the participants by a FraiLTI study team member. This will occur after member of the clinical care team has made the patient aware of the study and gain initial notification of interest in some cases there will be shared clinical and research roles at each recruiting site. It will be clearly stated that the participant is free to withdraw from the study at any time for any reason without prejudice to future care, and with no obligation to give the reason for withdrawal.

Written informed consent will then be obtained by means of participant dated signature and dated signature of the person who presented and obtained the informed consent. The person who obtained the consent must be suitably qualified and have been authorised to do so by the Chief Investigator as detailed on the Delegation of Authority and Signature log for the study. The original signed form will be retained at the study site within the Study Master File (SMF) or Investigator Site File (ISF). A copy of the signed Informed Consent will be given to participants and a copy retained in the participant medical notes. Written informed consent for participation in the study will be obtained by a doctor (SpR) or an appropriately qualified research nurse or research fellow (medically trained with appropriate consent training).

Study Methodology

Data collection

Baseline data:

The data collected will consist of patient demographics (including postcode for social-economic data), presenting symptoms, previous interventions and admissions in the past six months. Comorbidities were defined as per the Society of Vascular Surgery (SVS) guidelines where possible; diabetes was defined by documented medical history, the use of oral antidiabetic agents or insulin or fasting plasma glucose levels of at least 1.26 g/L; hypertension was defined by documented medical history and use of antihypertensive drugs for this purpose, or systolic blood pressure of at least 140 mmHg or diastolic blood pressure of at least 90 mmHg at admission determined by the average of the first two measurements. The following diseases were recorded based on

the patient's documented medical history: Ischaemic heart disease or prior myocardial infarction, atrial fibrillation, hypertension, cerebrovascular disease (stroke; including ischemic or haemorrhagic stroke as well as transient ischemic attack), end-stage renal failure requiring dialysis and a documented diagnosis of chronic obstructive pulmonary disease. The number of pre-operative drugs will also be recorded from the pre-assessment clinic documentation.

Routine clinical care laboratory test results (including haemoglobin, white-cell count, albumin, creatinine and eGFR, C-reactive protein and HbA1C) will be collected as well as height and weight.

**Axial imaging** by means of a CT-Angiogram (where performed) will enable measurement of skeletal muscle area at the L3 level (for comparison with previous studies), the mid-thigh and mid-calf levels (to enable detection of regional differences in muscle mass).

Physical performance will be measured by maximal grip strength will be measured using handgrip dynamometry, and the five times sit to stand test will be used to assess lower limb power. The Fried frailty score will be measured by combining five domains: weight loss (>4.5kg in last year), low grip (<27kg for men, <16kg for women), low walk speed (we anticipate that most participants will have restricted mobility and so will score a point automatically; a cut-off of <0.8m/s will be used for those that can undertake a 4m walk test), exhaustion (measured using two questions from the centre of epidemiologic studies depression scale (CES-D) scale used in the original Fried score) and low physical activity, measured using four activity questions used in the English Longitudinal Study of Ageing. A score of 3 or more will denote frailty, 1 or 2 prefrailty, and zero denotes non-frail. We will also collect information on, activities of daily living, nutritional intake, place of living and mobility aids as well as the Rockwood clinical frailty scale to provide comparison for robustness in this disease group. Participants will be invited to complete the Euro-QoL EQ5D-5L health status assessment.

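### The only biochemical route to a diabetes diagnosis is a fasting glucose that the data collection does not provide for, while the HbA1c that is collected has no role in the definition

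*Protocol*

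**What the plan says.** All of this is in the Protocol, Study Methodology, Data collection (Baseline data).

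- The comorbidity definitions open with a general rule: "Comorbidities were defined as per the Society of Vascular Surgery (SVS) guidelines where possible".
- Diabetes then has three alternative routes. The first is history: "diabetes was defined by documented medical history". The second and third are drug treatment and a laboratory value: "the use of oral antidiabetic agents or insulin or fasting plasma glucose levels of at least 1.26 g/L".
- The laboratory data are described shortly afterwards: "Routine clinical care laboratory test results (including haemoglobin, white-cell count, albumin, creatinine and eGFR, C-reactive protein and HbA1C) will be collected".

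Glucose is mentioned nowhere else in the protocol. HbA1c appears only in that laboratory list, with no threshold and no stated use. Under Aim, the primary aim "of the study is to identify the prevalence of frailty, sarcopenia and multimorbidity among chronic limb threatening ischaemia (CLTI) patients".

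**The concern.** The definition and the data collection do not match. The definition relies on a test that the protocol does not name for collection, and the glycaemic test that it does name is not in the definition.

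Two things are at stake. First, multimorbidity prevalence is part of the primary aim, and diabetes is one of the few comorbidities that the protocol defines explicitly. The protocol does not list the conditions that make up multimorbidity, so including diabetes is an inference, though a natural one. Second, diabetes is an obvious covariate for limb loss under the secondary aim. If some centres happen to have a fasting glucose on file and others do not, the same patient could be coded differently depending on where he or she was admitted.

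**Working it through.** **Inputs.** The diabetes definition and the laboratory list come from Baseline data, the routes of entry from Recruitment, and the planned total of 200 from Sample-size. The molar mass of glucose (180.156 g/mol) is used only to check units.

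**Step 1: is the threshold itself sound?** 1.26 g/L ÷ 180.156 g/mol × 1000 = 6.99 mmol/L, which is 126 mg/dL. There is no unit error. The problem is availability of the test, not the cut-off.

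**Step 2: definition against data collection.**

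| Item | In the diabetes definition? | Named for collection? |
|---|---|---|
| Documented history | Yes | Yes (comorbidities are baseline data) |
| Antidiabetic drugs | Yes | By implication; only the number of drugs is separately listed |
| Fasting plasma glucose | Yes | No; no fasting sample or fasting status either |
| HbA1c | No | Yes |

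Patients may enter from clinics, the emergency department or a GP referral, and the laboratory data are limited to what routine care produces. Nothing therefore ensures that a glucose on file was taken fasting, or that its fasting status is known.

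**Step 3: who is affected if the text is followed as written?**

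- History or drug treatment present: coded diabetic, whatever the laboratory data. Not affected.
- Neither present, fasting glucose on file at or above the threshold: coded diabetic. Not affected.
- Neither present, no fasting glucose on file, HbA1c in the diabetic range: coded non-diabetic, although a collected result indicates otherwise. Affected.
- Neither present, and neither test on file: coded non-diabetic. A change of definition cannot help here.

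**Step 4: size.** The protocol gives no rate of undiagnosed diabetes, no share of patients with a fasting glucose on record and no HbA1c coverage. The count can only be written as a formula:

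missed = N × u × (1 − f)

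Here N = 200, u is the share of participants with undiagnosed diabetes, and f is the share of those with a usable fasting glucose. With u assumed to be 1% to 10%, purely to show the range:

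- f = 0: 200 × 0.01 = 2 to 200 × 0.10 = 20
- f = 0.5: 1 to 10
- f = 1: 0

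The range from 0 to 20 reflects the assumptions and is not an estimate. Only those missed participants who have an HbA1c result in the diabetic range could be recovered by using it.

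**The case against.** The best defence is that this is a small wording gap. Fasting glucose is only one of three alternatives, so known and treated diabetes is captured without any laboratory value. Most of the neighbouring conditions are recorded from documented history, so a mainly history-based diabetes variable is not out of line. The laboratory list is introduced as *including* the named tests, so a glucose could be collected where measured, and the definitions apply only *where possible*. A diabetic-range HbA1c found in routine care may also lead to a documented diagnosis, which the history route would then pick up.

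Most of this stands, and it limits the point to undiagnosed diabetes. It does not remove the mismatch. An open-ended list of routine results does not supply a fasting sample or a record of fasting status, and it leaves centres free to ascertain the variable differently. The guideline citation does not settle the matter either: reference 12, attached to it, is listed as a study of anaemia and one-year mortality after acute myocardial infarction.

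A reader might infer three stronger things that the document does not support:

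- *That undiagnosed diabetes will certainly be missed, or that the glucose field will be empty for most participants.* The protocol gives no information on coverage.
- *That HbA1c goes unused in the study.* This is established only for the definition. The statistical analysis plan is not at hand, and the values will be in the dataset where measured.
- *That the drug route is also faulty because, unlike hypertension with "documented medical history and use of antihypertensive drugs for this purpose", it does not specify the indication.* That is a matter of preference, and it would over-count diabetes rather than miss it. It is not part of this point.

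**Conclusion.** The mismatch is real and modest. The one biochemical criterion for diabetes is not supported by the stated data collection, and the glycaemic marker that is collected is left out of the definition. As a result undiagnosed diabetes may be missed or ascertained inconsistently between centres, including in participants whose collected HbA1c would show it.

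The number affected cannot be derived from the protocol. The point concerns one comorbidity. Its bearing on the primary aim assumes that diabetes counts towards multimorbidity, and even then recoding it changes multimorbidity status only for participants at the margin of whatever count is used. The frailty prevalence estimate and the sample size, which rests on frailty, are unaffected. The point is still worth correcting before data collection, because fasting status that was never recorded cannot be recovered later, and using HbA1c afterwards would mean departing from the protocol's own definition.

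**What to change.** Reconcile the diabetes definition with the laboratory list in Baseline data:

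1. Add the HbA1c already collected, at a pre-stated laboratory diagnostic threshold in mmol/mol, as a further alternative route to the diabetes variable.
2. Keep the fasting-glucose route, but apply it only where a value recorded as fasting exists.
3. Flag HbA1c values from participants with anaemia, recent transfusion or dialysis.
4. Report a sensitivity analysis with diabetes coded on history and drugs alone.

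HbA1c should be added and should not replace glucose, and anaemia belongs in the flag. Anaemia is one of the study's own exposures, so relying on HbA1c alone without that flag would tie diabetes misclassification to a factor under study.

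The cost is a wording change, a flag in the dataset and one extra analysis, with no new test. The downside is that HbA1c is less reliable in the flagged participants and will be missing where routine care did not measure it. The number of participants with each laboratory result should therefore be reported beside the diabetes prevalence.

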#### Procedure and discharge related data:

Following the baseline data capture, details on any surgical or endovascular procedure performed, the total duration of hospital admission, the discharge environment or package of care and mobility will be recorded. All patients who agree to participate will be followed up irrespective of whether they undergo any revascularisation.

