# Sample-size

This study seeks to gather preliminary data to enable future sample size calculations. Although an accurate sample size calculation is not possible without such pilot data, we estimate that a sample size of 200 participants would be sufficient to detect a frailty prevalence of 25% with a precision of +-5% (i.e. 95% CI 20% to 30%). This prevalence is a conservative estimate, based on our local retrospective data for sarcopenia, where the prevalence is approximately 25% of CLTI patients. Frailty rates are estimated to be similar or higher. We aim to recruit a minimum of 40 patients per centre from a minimum of five centres giving a total of 200 patients. So far through national enquiry 10 UK vascular centres have agreed to participation following successful ethical approval. Through our collaborative work we have also been approached by the Fiona Stanley Hospital, Perth, Australia as potential collaborator.

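### The drug count behind the polypharmacy objective has no defined source for participants who bypass pre-assessment or are never operated on, so it is likely to be missing selectively by pathway.

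*Protocol*

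**What the plan says.** The study summary gives the secondary objective as "To understand if frailty, multimorbidity and poly pharmacy are associated with adverse clinical outcomes". Polypharmacy is thus one of three exposures to be related to amputation, survival, re-intervention, length of stay, discharge home and re-admission.

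The drug count is described once, in Study Methodology, Data collection, under baseline data: "The number of pre-operative drugs will also be recorded from the pre-assessment clinic documentation". No second source is given, and nothing is said about participants without such a record. The next paragraphs of the same section do allow for availability in another measure: axial imaging is "by means of a CT-Angiogram (where performed) will enable measurement of skeletal muscle area".

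The population is set out in four places:
- Recruitment: "All presentation modes will be eligible including out-patient clinic, emergency clinic, emergency department and general practitioner referrals".
- Inclusion: "All chronic limb-threatening ischaemia patients as per consensus definition irrespective of mode or presentation or plan to revascularize".
- Procedure and discharge related data: "All patients who agree to participate will be followed up irrespective of whether they undergo any revascularisation".
- Aim, where the secondary aim covers outcomes such as "re-admission as well as those with non-salvageable CLTI".

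**The concern.** The named source belongs to a planned-surgery pathway, but the eligibility rules require neither a planned admission nor an operation. Sites that follow the instruction as written will have a count for participants who passed through pre-assessment and may have none for the rest. Whether a value is present then depends on how the patient arrived and what was decided about treatment.

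At stake is the polypharmacy part of the secondary objective. An association estimated from participants with a count would be reported for an all-comers CLTI cohort while resting mainly on planned surgical patients. Non-salvageable disease, in which the protocol declares an interest, is a group where a pre-operative record is least assured. A later analysis plan can say how missing counts are handled, but it cannot supply values that were never collected.

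**Working it through.** **The plan's own figure.** The protocol states no figure for the drug count or for the share of participants with a pre-assessment record, so there is nothing to reproduce on this point. The two recruitment totals serve only as denominators: 40 × 5 centres = 200 (Sample-size) and about 30 × 10 centres = 300 (study summary).

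**Step 1: source against population.**
- The source assumes attendance at a pre-assessment clinic. Recruitment admits patients from the emergency department and emergency clinic, for whom no such visit is implied.
- The variable is defined relative to an operation. Inclusion and the procedure section keep participants for whom no revascularisation is planned or performed. For those never operated on, the count is undefined even where a drug list exists.
- The CT measure carries an availability caveat and the drug count does not, so the text gives no sign that the gap was foreseen.

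**Step 2: is the gap selective?** If a record is absent because of route or operative status, the absence is not random across the cohort. The protocol itself treats route as relevant: Recruitment says that taking all routes will inform on referral mode in the context of frailty. Operative status bears on listed outcomes such as re-intervention and length of stay.

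**Step 3: participants left with a count (missing share m is assumed).** Number left = N × (1 − m).
- m = 10%: 200 × 0.9 = 180; 300 × 0.9 = 270
- m = 20%: 160; 240
- m = 40%: 120; 180
- m = 60%: 80; 120

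**Step 4: what selectivity could do to a simple summary (all inputs assumed).** Let polypharmacy prevalence be p₁ in those with a record and p₂ in those without. The complete-case estimate is p₁ and the cohort value is p₁(1 − m) + p₂m, so the error is −m(p₂ − p₁).
- p₁ = 50%, p₂ = 70%: −4, −8 and −12 percentage points at m = 20%, 40% and 60%
- p₁ = 50%, p₂ = 60%: −2, −4 and −6 points
- p₁ = p₂: no error at any m

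**Step 5: the association.** The objective concerns an association, so Step 4 shows the mechanism and does not estimate the bias in that association. The association among participants with a record applies to the whole cohort only if it is the same across pathways. That could not be checked, because the participants needed for the check would be the ones without a count.

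**The case against.** Naming one source does not forbid others. The baseline section defines diabetes and hypertension partly through drug use for all participants, so some medication history is expected whatever the pathway, and a sensible site might use it. The scope is also narrow. Polypharmacy appears in the summary's secondary objective but not in the study title or the Aim section, and the Sample-size section describes the study as gathering preliminary data. These points limit the weight of the concern. They do not remove it: knowing that a patient takes an antihypertensive does not give a drug count, and a site that improvises leaves the variable defined differently from place to place.

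A reader might also infer several stronger things that the documents do not support:
- **That the count is missing in the sickest participants, who carry excess deaths and amputations.** No section ranks emergency or non-operated participants by severity. Non-operated patients could include milder disease, and eligibility already requires the ability to consent and complete assessments.
- **That 60 to 120 of 200 participants would have no count.** This takes an assumed 30% to 60% unscheduled or non-operated and supposes that every one of them lacks a value. Neither step is in the protocol.
- **That the frailty estimate would lose the same participants.** The Statistical Analysis section says only that several variables will be tested. It neither places the drug count in a model with frailty nor specifies complete-case analysis.
- **That admission drug records are already being reviewed.** Record review is described for 90-day outcomes, and no drug chart is mentioned.

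**Conclusion.** The concern holds in a limited form. The stated source and the pre-operative definition do not fit the stated population. Followed as written, they leave the drug count undefined for participants not operated on and likely to be missing by admission route and operative status.

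The consequence is confined to the polypharmacy part of the secondary objective, whose result would mainly describe planned surgical patients. The primary frailty prevalence does not use this variable and is unaffected. The size cannot be derived from the documents, and the missing shares and prevalences in the working are assumptions that show a range.

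The mismatch itself rests only on the protocol's text. Its practical effect rests on the inference that some emergency and non-operated participants have no pre-assessment record. This is an error in a stated data-collection rule, so it belongs in the protocol and cannot be left to an analysis plan.

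**What to change.** Redefine the variable as the number of regular drugs on admission, before any in-hospital change, and require it for every participant whatever the route or treatment plan. Take it from a source available for all inpatients, for example the admission medicines record. Allow pre-assessment papers as a fallback, and add a CRF field for the source used so that completeness and counts can be compared by source.

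The change needs one protocol sentence and one CRF definition with the added field. The costs are a small amount of extra extraction at sites and some variation in the count between sources, which the source field makes visible. It should be made before data collection, since a count not taken at baseline may be hard to recover later.
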